1. General Information / Title Page

Title: Intratympanic Steroid Injection for Treatment of Idiopathic Facial Nerve Paralysis

Working Title: Facial Nerve Study

Project #: 2007139

Version #: 1

Date: 11/21/16

Sponsor: *None*

Faculty Primary Investigator: *[name]*
University of Missouri
Department of Otolaryngology – Head & Neck Surgery
[name]
[name]

Resident Co-Investigator: *[name]*
University of Missouri - Resident Physician
Department of Otolaryngology – Head & Neck Surgery
[name]
[name]

The study will be conducted in accordance with the design and specific provisions of this IRB approved protocol, in accordance with the ethical principles that have their origin in the Declaration of Helsinki, and that are consistent with Good Clinical Practice (GCP) and the applicable regulatory requirement(s). The Principal Investigator will assure that no deviation from, or changes to, the protocol will take place without prior agreement from the sponsor and documented approval from the IRB, except where necessary to eliminate an immediate hazard(s) to the trial participants. The Principal Investigator will promptly report to the IRB and the sponsor any changes in research activity and all unanticipated problems involving risk to human subjects, or others. This trial will be performed in compliance with the protocol, GCP, and all regulatory requirements.

2. Schedule of Events

Recruitment of trial subjects will begin as soon as authorization is granted by the IRB. Clinic and emergency department patterns indicate that we can expect to identify and enroll 20- 25 participants per year. The goal of the study is to include 90 participants over the course of four years and follow until full facial nerve function is recovered or up to 12 months after the completion of treatment, whichever comes first. The expected length of the entire study will vary depending on when all subjects are identified and treatment is completed.

After obtaining consent, the study participant will undergo a complete history, head, neck, and cranial nerve exam. Facial function will be evaluated with House-Brackmann (H-B) scoring system. For participants with a high suspicion of Lyme disease based on history, Lyme disease serology will be drawn. Electroneurography (ENoG) and electromyography (EMG) testing will be performed on patients with complete facial nerve paralysis. Every participant will be treated with oral steroids (prednisone 60 mg for 5 days followed by a 5 day taper), unless they are unable to for medical reasons.

The study participants will then be randomized into the control group or the treatment group. If randomized to the treatment group, the patient will undergo one intratympanic steroid injection every 3-4 days over the course of 3 weeks for a total of 3 injections. A third group of patients will include those patients that are unable to take oral steroids for medical reasons (such as diabetes); these patients will only receive the intratympanic injection. An audiogram and tympanography testing will be performed on patients that are randomized to receive an intratympanic injection (Group 2) or are placed in Group 3 for medical reasons.

3. Abbreviations

All abbreviations will be defined in parenthesis following their first occurrence in the text.

4. Background Information

Facial nerve paralysis is due to inflammation surrounding the facial nerve. Current clinical practice guidelines for treatment of facial nerve paralysis recommend a 10 day course of oral steroids +/- oral acyclovir. Treatment should begin within 72 hours of symptom onset. In patients with complete facial paralysis, electrodiagnostic testing should be offered to the patient (1-2). In patients with 90% degeneration on electroneuronography (ENoG) testing, facial nerve decompression may be considered but is not a current recommendation.

In 1973, Bryant reported on ten cases where intratympanic steroid injection was used for the treatment of Bell's palsy (3). All but one of these patients had complete recovery of their facial nerve function. The remaining patient had 75% recovery. None of these patients suffered complications from the injections. The next study published on intratympanic steroid injection

for Bell's palsy was not published until 2014 (4). It was a randomized control trial that divided patients into standard treatment (oral steroids and acyclovir) versus standard treatment with intratympanic steroid injection. There was not a statistically significant difference between the complete recovery rate of the control group and of the intratympanic steroid group; however, the time to recovery was significantly shorter in the intratympanic steroid injection group as compared to the control group. Limitations of this study include small sample size and high attrition rate.

There have not been any other studies published in the literature looking at improving facial nerve recovery in idiopathic facial nerve paralysis with the use of intratympanic steroid injections.

5. Trial Objectives and Purpose

The question proposed by this study are:

Does intratympanic steroid injection improve the complete recovery rate of patients with idiopathic facial nerve paralysis?

Does intratympanic steroid injection hasten the time to recovery in patients with idiopathic facial nerve paralysis?

Are there significantly more adverse effects with the use of intratympanic steroid injection as compared to oral steroids in patients with idiopathic facial nerve paralysis?

The trial seeks to provide evidence that intratympanic steroid injection are acceptable and successful adjuncts to treatment of idiopathic facial nerve paralysis.

To answer this question, a prospective, single-blinded, randomized trial will be performed. The subjects will be randomized into the treatment group and the control group. The control group will receive oral steroids which is the current standard of care. Patients in the treatment group will receive oral steroids AND intratympanic steroid injections. The patient's will not be blinded because the patient will be undergoing an in-office procedure. It has been found to be unethical to perform sham procedures in patients. A third group of patients will consist of those patients that are unable to take oral steroids for medical reasons. These patients will only receive the intratympanic injection and they are placed in this group for medical reasons only (no randomization into this group). The patients will be examined and scored using House-Brackmann scoring system by a blinded investigator trained in otolaryngology.

6. Trial Design

Design:

Prospective, randomized, single-blinded clinical trial

Protocol: *Facial Nerve Study*

PI: [name]

End Points:

Complete recovery of facial nerve function

Time to complete recovery of facial nerve function

Improvement of facial nerve function within 3 weeks

Time to initial improvement of facial nerve function

Adverse effects related to the treatment

Methodology:

Screening

Patients age 18-99 will be identified in clinic as having an acute facial nerve paralysis of H-B IV or greater. Symptoms must have developed within a 72 hour period and be present for the last 21 days or less.

Baseline assessment

Patients who meet criteria will undergo a complete history, head, neck, and cranial nerve exam. Facial function will be evaluated with H-B scoring system. In patients where there is a suspicion of Lyme disease, Lyme disease serology will be performed. Electroneurography (ENoG) and electromyography (EMG) testing will be performed on patients with complete paralysis only.

Treatment Phase

Participants in groups 1 & 2 will be treated with steroids (prednisone 60 mg for 5 days followed by a 5 day taper). Patients will then be randomized into either control group (Group 1) or treatment group (Group 2). Patients in Group 2 will undergo intratympanic steroid injection. An audiogram and tympanography testing will be performed prior to injections.

Participants unable to take oral steroids for medical reasons (such as diabetes) will be placed in Group 3. These participants will receive intratympanic steroid injections only. An audiogram and tympanography testing will be performed prior to injections.

Injection will be up to 1cc of dexamethasone 24mg/mL. The procedure will be performed at supine position under a microscope. Local anesthesia will be achieved with topical phenol. A myringotomy will be made in the tympanic membrane. A 1 mL syringe connected to a needle will be used to slowly inject between 0.2 cc and 1.0 cc of solution through the myringotomy, with the subject's head turned 45 degrees to the opposite side. The subject will be asked to maintain positioning for at least 30 minutes and refrain from swallowing. The dose administered will vary due to subject-specific factors.

Follow-Up

Patients will be evaluated once a week for the first month after completion of treatment. From that point, patients will be evaluated monthly until complete recovery.

Procedures:

Participants are identified in clinic to have idiopathic facial nerve paralysis. If they meet inclusion criteria, they will then be asked to participate in the study and sign the consent form. Participants will undergo a complete medical history including facial nerve paralysis history, head, neck, and cranial nerve exam. Facial function will be evaluated with H-B scoring system. Lyme disease serology will be drawn on patients for which there is a suspicion of Lyme disease (SOC). Electroneurography (ENoG) and electromyography (EMG) testing will be performed only on patients with complete paralysis, as part of the standard of care (SOC) work-up. Next, patients in Groups 1 & 2 will be prescribed a course of oral prednisone. They will be randomized to Group 1 or Group 2. If randomized to Group 1, patient will come back weekly for a month for evaluation of facial nerve function. If randomized to Group 2 or placed into Group 3, patients will undergo an audiogram and tympanometry testing, which is SOC prior to any intratympanic injection. Patients will undergo intratympanic steroid injection to affected side after all details and risks of each procedure are discussed. There will be one injection every 3-7 days over the course of 3 weeks for a total of 3 injections. Follow-up will be once a week for the first month after the completion of treatment. From that point, patients will be evaluated monthly. All patients Group 2 & 3 will undergo a post-procedure audiogram and tympanogram approximately 1 month following the 3rd injection, which is SOC. Follow-up will be completed once full facial nerve recovery to H-B I or for up to one year, whichever comes first. At each clinic visit patients will undergo a complete head and neck exam, including H-B score. Extensive review of systems will be completed at every visit. Facial nerve exams will be video recorded pre-treatment and all post-treatment follow-up visits to allow for 2 independent blinded reviewers to determine facial nerve recovery and H-B score; a third unblinded review will be performed by the treating physician.

Adverse effects of the treatment will be assessed at each visit.

7. Selection and Withdrawal of Subjects

Inclusion Criteria:

1. 18 to 99 years
2. English as primary language
3. Acute unilateral facial palsy without skin lesions which developed within a 72-hour period and is present for 21 days or less.
4. Moderate to severe facial palsy [House-Brackmann grade IV or greater]

Protocol: *Facial Nerve Study*

PI: [name]

Exclusion Criteria:

1. Another cause of facial nerve paralysis that is not idiopathic
2. Otologic disease including otitis media, temporal bone fracture, a previous history of facial nerve palsy in either side, history of otologic surgery, and suspected Ramsay Hunt syndrome.
3. Systemic disease including history of tuberculosis, history of head and neck cancer, other neurological disorders, recent use of ototoxic medications, liver or renal dysfunction, and other illnesses that would contraindicate the use of high-dose steroid therapy.
4. Pregnancy

Withdrawal Criteria:

Subjects may withdraw from the study at any time without prejudice to their care. They may also be discontinued from the study at the discretion of the Investigator for lack of adherence to study treatment or visit schedules or adverse events. The Investigator may also withdraw subjects who violate the study plan, or to protect the subject for reasons of safety or for administrative reasons. It will be documented whether or not each subject completes the clinical study. If the Investigator becomes aware of any serious, related adverse events after the subject completes or withdraws from the study, they will be recorded in the source documents and on the case report form.

8. Treatment of Subjects

Participants in Groups 1 & 2 will be treated with steroids (prednisone 60 mg for 5 days followed by 5 day taper) as defined by the current standard of care. Patients in Group 1 will not have any further treatment. Patients in Group 2 & 3 will undergo intratympanic steroid injection. The patient will undergo one injection every 3-7 days over the course of 3 weeks for a total of 3 injections.

9. Costs

Participants will not be paid to be a part of the study. Subjects will be responsible for the normal cost of treatment associated with facial nerve paralysis, including any tests that the physician feels are necessary and all medications. Subjects who are randomized to one of the groups to receive the intratympanic injections will not be responsible for the added costs of the injection (which include the medication and phenol), the audiogram and tympanometry, and extra office visits to receive each injection.

10. Assessment of Efficacy

Efficacy of the treatment will be assessed by measuring facial nerve function using the H-B scale I-VI. Two blinded trained otolaryngologist or mid-level provider trained in otolaryngology will determine the efficacy by evaluating each individual study subject via video recording.

10. Assessment of Safety

Risks of intratympanic steroid injections include pain, bleeding, vertigo, otitis media, and tympanic membrane perforation.

The presence or absence of tympanic membrane perforation will be documented at 14 days and 1 month post-treatment. If a perforation is present, the extent of the perforation, type of treatment, and when resolved will be recorded.

All adverse events will be reported to the IRB and the Otolaryngology Department Quality Assurance. Admission of a trial participant to an emergency room or hospital will be recorded.

11. Statistics

A sample calculation was performed for the number of subjects to be enrolled in order to prove superiority of oral steroids + intratympanic steroids over oral steroids alone. The assumption was made that a 20% increase in primary outcome of complete recovery would be significant. A sample size of 25 subjects should detect a difference at a power greater than 80% and an alpha of 0.05. To account for potential testing or data collection errors, we will collect data on 30 subjects treated with oral steroids and intratympanic steroid injections, as well as 30 controls treated with oral steroids only, for a total of 60 subjects. Data will be collected on up to 30 additional subjects that are placed into Group 3 for medical reasons; therefore total number of subjects to be recruited is 90.

12. Direct Access to Source Data/Documents

The investigators will permit study-related monitoring, audits, IRB/IEC review, and regulatory inspection(s) by providing direct access to source data/documents.

13. Quality Control and Quality Assurance

The integrity of the data collected will be maintained by the randomization of trial subjects to their groups (*control vs. treatment*). All subjects are being treated using standard protocols. Even though participants will not be fully blinded, the data collected is reliable because it is randomized and objective measures will be obtained. Objective measures for this study include complete recovery of facial nerve function, time to complete recovery of facial nerve function, improvement of facial nerve function within 3 weeks, and time to initial improvement of facial nerve function. The University's biostatistics group can view any data collected prior to publication.

14. Ethics

A randomized study involving the adult population is subject to ethical as well as scientific considerations. The patients will not be blinded because it is unethical to perform a sham procedure. HIPAA guidelines will be followed in order to protect the privacy of study participants. The Otolaryngology community stands to benefit significantly from this study, as results will potentially yield information which will be used to improve outcomes of patients with facial nerve paralysis as this can be a debilitating disease process.

15. References

3. Bryant FL. Intratympanic injection of steroid for treatment of facial paralysis. *Laryngoscope.* 1973 May;83(5):700-6. PubMed PMID: 4702471.

Protocol: *Facial Nerve Study*

PI: [name]

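### All participants able to take oral steroids are prescribed a 10-day prednisone course with entry open to day 21, and nothing accounts for oral steroids already taken for the same episode

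*Combined protocol and SAP*

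**What the plan says.** All references are to the combined protocol and SAP.

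- **Treatment.** Section 2: "Every participant will be treated with oral steroids (prednisone 60 mg for 5 days followed by a 5 day taper"; the one exception is a participant who medically cannot take them. Section 6 (Procedures), after consent and the baseline examination: "Next, patients in Groups 1 & 2 will be prescribed a course of oral prednisone". Section 8 gives the same course to Groups 1 and 2 and describes it "as defined by the current standard of care". None of these passages makes the prescription depend on treatment already received.
- **Guideline care as the protocol cites it.** Section 4: "Current clinical practice guidelines for treatment of facial nerve paralysis recommend a 10 day course of oral steroids +/- oral acyclovir", and "Treatment should begin within 72 hours of symptom onset".
- **Entry window.** Section 7, third inclusion criterion: "Acute unilateral facial palsy without skin lesions which developed within a 72-hour period and is present for 21 days or less". Screening in section 6 has the same limit.
- **Prior medication.** The only earlier medication that the section 7 exclusions name is recent ototoxic drugs. Oral steroids for the present episode appear in neither list of criteria.
- **Baseline data.** Section 6 asks for a general medical history that covers the facial palsy. It names no item for earlier treatment.
- **Analysis.** Section 11 contains the sample-size paragraph only. No stratification factor, covariate or subgroup is stated anywhere.

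**The concern.** The protocol describes care in which oral steroids start within three days, admits patients up to three weeks after onset, and then prescribes a course to all who can take it. These statements fit together only if no entrant has been treated before enrolment, and nothing in the criteria ensures that.

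Two things are at stake. The first is exposure. A participant who has started or finished a course would be prescribed another, and the text gives the investigator no instruction for that case. This also blurs the third objective in section 5, which compares the adverse effects of injection with those of oral steroids.

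The second is interpretation. The randomised groups may mix patients on a first course with patients on a repeated or overlapping one, and the plan offers no way to tell them apart. That affects complete recovery, and also improvement within 3 weeks and time to improvement, which are listed as end points in section 6.

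**Working it through.** **1. The plan's own course length.** Section 2: 5 days + 5-day taper = 10 days. This agrees with the 10-day course cited in section 4.

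**2. Timing.** Inputs: latest guideline start, day 3 (section 4); course length, 10 days; last entry day, 21 (section 7).

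- Latest end of a guideline course: 3 + 10 = about day 13. A course begun sooner ends sooner.
- Entry days after that: 14 to 21, which is 21 - 13 = 8 days of the window. For entry on those days a guideline-treated patient has finished a course. Before then the patient is part-way through one or has just finished.
- Largest total exposure under the rule: 10 + 10 = about 20 days, against 10.

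**3. Chance imbalance between the randomised arms.** Input: 30 per arm (section 11). The documents give neither the pre-treated share *f* nor the difference *g* in complete recovery between untreated and pre-treated patients. Both are assumed: *f* from 10% to 50%, *g* from 10 to 30 points.

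- SD of the difference in pre-treated share between arms = sqrt(2 × f × (1 - f) / 30)
- 95% limit of the shift in the arm difference = 1.96 × SD × g

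For example, at *f* = 30%: sqrt(2 × 0.3 × 0.7 / 30) = 0.118; 1.96 × 0.118 = 0.232; with *g* = 30 points, 0.232 × 30 = 7.0 points.

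| Assumed share f | SD (points) | 1.96 × SD (points) | Shift, g = 10 | Shift, g = 20 | Shift, g = 30 |
|---|---|---|---|---|---|
| 10% | 7.7 | 15.2 | 1.5 | 3.0 | 4.6 |
| 30% | 11.8 | 23.2 | 2.3 | 4.6 | 7.0 |
| 50% | 12.9 | 25.3 | 2.5 | 5.1 | 7.6 |

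Exact binomial probabilities for 30 versus 30: at shares of 20%, 30% and 50%, the arms differ by at least 10 points in pre-treated share with probability 0.42, 0.48 and 0.52, and by at least 20 points with probability 0.07, 0.12 and 0.16.

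**4. How much of the trial's error this is.** Assume 75% complete recovery, a rate that the documents do not give. The SE of the unadjusted difference is sqrt(2 × 0.75 × 0.25 / 30) = 0.112, or 11.2 points, so the 95% range is about ±22 points. With *f* = 30% and *g* = 30 points, the imbalance contributes an SD of 0.118 × 30 = 3.5 points, and (3.5 / 11.2)² is about 10% of the variance. With *g* = 10 points the SD is 1.2 points, about 1%.

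The target in section 11 is a 20% increase in complete recovery. Read as absolute points, which section 11 does not specify, the largest shift in the table is 7.6 / 20 = 38% of it and the smallest is 1.5 / 20 = 8%.

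**The case against.** The strongest reply is that this is an omission with little statistical consequence. Patients may arrive untreated: section 6 says they are identified in clinic, and section 2 mentions the emergency department only in an enrolment forecast. Both randomised groups receive the same oral course, so the contrast remains the added injection in whoever is enrolled. Chance imbalance in any baseline factor is already covered by the standard error. The palsy history would be a natural place to note earlier treatment. Section 7 excludes illnesses that contraindicate high-dose steroids and lets the investigator withdraw a subject for safety.

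Much of this stands, and it rules out several stronger readings that a reader might infer:

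- *Pre-treated entrants have failed steroids or are non-responders.* The primary outcome is complete recovery, with follow-up of up to 12 months. House-Brackmann grade IV or worse in the second or third week is not failure on that scale, and some entrants would still be mid-course.
- *A strong prognostic factor is lost.* The documents give no recovery rate by prior steroid use, so its strength is unknown.
- *Eight in 21 entrants are affected.* That ratio counts days in the window. The documents do not give the distribution of entry days or the share treated beforehand.
- *The Group 1 versus Group 2 comparison is biased.* Randomisation prevents systematic bias. What remains is random and is partly removable by adjustment.

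The reply does not remove the conflict in the text. Section 6 has the course prescribed after consent and examination, so a course taken earlier cannot simply be read as the trial course. A general history is not a data item, and neither the contraindication exclusion nor the withdrawal clause says what happens when a course has already been started or finished.

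**Conclusion.** The point holds as a conflict between passages with a modest statistical cost. Followed literally, sections 2, 6 and 8 repeat or overlap a course for anyone already treated as section 4 describes, with up to about 20 days of exposure instead of 10. This needs only the protocol's own figures. How often it would happen cannot be judged from the documents.

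For the randomised comparison, the harm is added heterogeneity, a less clear interpretation and chance imbalance. The 1.5 to 7.6 point range rests on the assumed shares and deficits above. It is a 95% limit and not an expected error, and it must not be added to the trial's stated uncertainty. The point does not depend on whether the sample size in section 11 is adequate, which is a separate matter.

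**What to change.** 1. In the baseline history, record the start date and number of days of any oral steroid taken for this episode.
2. Pre-specify prior oral steroid (yes/no) as a covariate in the Group 1 versus Group 2 comparison of complete recovery. Section 11 names no analysis, so the adjusted comparison has to be written in, for example a logistic model with terms for arm and prior steroid.
3. Report the result without pre-treated participants only as a sensitivity analysis of low power. At assumed shares of 10%, 30% and 50%, about 27, 21 and 15 per arm would remain (30 × 0.9, 30 × 0.7, 30 × 0.5).
4. The investigators must reconcile sections 2, 6 and 8 with the 21-day window and the 72-hour statement, and state what a participant who has started or finished a course receives. This review proposes no clinical rule. Steps 1 to 3 do not settle the question of repeat exposure; only this step does.

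The cost is one item in a history already taken, one model term, a clarifying sentence in the treatment passages, and reduced numbers in the sensitivity analysis. No extra visit or participant is needed.

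### Safety is posed only as a significance question that 30 patients per arm can rarely answer; harms should be estimated as rates with confidence intervals

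*Combined protocol and SAP*

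**What the plan says.** Section 5 lists three questions. The third, on safety, asks: "Are there significantly more adverse effects with the use of intratympanic steroid injection as compared to oral steroids". The next sentence gives the overall purpose: "The trial seeks to provide evidence that intratympanic steroid injection are acceptable and successful adjuncts to treatment of idiopathic facial nerve paralysis".

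Section 6 lists treatment-related adverse effects among the end points and has them assessed at each visit. It also describes each injection as given through a myringotomy. Section 8 says that Group 1 has no treatment beyond oral prednisone.

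The Assessment of Safety section (the second of two sections numbered 10) names the harms: "Risks of intratympanic steroid injections include pain, bleeding, vertigo, otitis media, and tympanic membrane perforation". Perforation is documented at 14 days and at 1 month, with its extent, treatment and resolution. All adverse events go to the IRB and to departmental quality assurance, and emergency room and hospital admissions are recorded.

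Section 11 sizes the trial on complete recovery alone: "A sample size of 25 subjects should detect a difference at a power greater than 80% and an alpha of 0.05". It then says that "we will collect data on 30 subjects treated with oral steroids and intratympanic steroid injections, as well as 30 controls", plus up to 30 non-randomised patients in Group 3. For harm it gives no test, sidedness, expected rate, margin, acceptability limit or confidence interval.

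**The concern.** Question 3 is the only criterion in the plan that bears on the safety half of the word acceptable, and it is a significance criterion in a trial that was not sized for harm. The risks named in the safety section are risks of the injection itself. For perforation caused by the procedure, Group 1 can contribute essentially no events, so a test against Group 1 says little that a clinician needs. The useful figure is how often the harm occurs per injected patient, and how precisely that is known.

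At stake is the safety conclusion. An injection-caused harm affecting one patient in ten would usually be followed by a statement that adverse effects were not significantly more frequent. Placed beside the stated aim, that statement could be misread as support for acceptability.

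**Working it through.** **The plan's own figure.** The plan gives none for safety. Its only sizing figure is 25 subjects for a 20% increase in complete recovery, with no control rate stated. Taking 25 as per arm and the increase as 20 points, the two-sided pooled two-proportion formula at 80% power gives 49 to 97 per arm for control rates of 75% down to 40%, so 25 is not reproduced at those rates. It is approached only near the ceiling: for 80% against 100%, one-sided and unpooled, (0.80 × 0.20 + 0) × (1.645 + 0.842)² / 0.20² = 24.7, that is 25. That is a separate matter, and nothing below depends on it.

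**Inputs.** 30 per randomised arm and alpha 0.05 (section 11; alpha is stated for efficacy only, without sidedness). Assumption: 0/30 events in Group 1 for a harm that only the procedure can cause. The true harm rate is also an assumption, swept below because the plan gives none.

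**Step 1: events needed for significance.** Against 0/30, the two-sided Fisher p-value for k events is 2 × C(30,k) / C(60,k):
- k = 4: 2 × 27,405 / 487,635 = 0.112
- k = 5: 2 × 142,506 / 5,461,512 = 0.052
- k = 6: 2 × 593,775 / 50,063,860 = 0.024

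Two-sided Fisher therefore needs 6/30. Other tests give:

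| Test | Smallest significant count | p there | p at one fewer |
|---|---|---|---|
| Two-sided Fisher | 6/30 (20%) | 0.024 | 0.052 |
| Chi-square with Yates correction | 6/30 (20%) | 0.031 | 0.062 |
| One-sided Fisher | 5/30 (17%) | 0.026 | 0.056 |
| Boschloo | 5/30 (17%) | 0.022 | 0.053 |
| Uncorrected chi-square | 4/30 (13%) | 0.038 | 0.076 |

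The range is 4 to 6 of 30. Halving the uncorrected chi-square p-value for a one-sided test would admit 3/30 (0.0756 / 2 = 0.038), but with 3 / 2 = 1.5 expected events per arm that approximation is not one to rely on.

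**Step 2: chance of reaching significance.** With X binomial (30, true rate), P(X ≥ k) is:

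| True rate | k = 4 | k = 5 | k = 6 |
|---|---|---|---|
| 5% | 6% | 2% | 0.3% |
| 10% | 35% | 18% | 7% |
| 15% | 68% | 48% | 29% |
| 20% | 88% | 74% | 57% |

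A true 10% harm is thus missed about 65% to 93% of the time. An 80% chance of significance needs a true rate of about 18% (k = 4), 21% (k = 5) or 25% (k = 6).

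**Step 3: what an interval would show.** Exact (Clopper-Pearson) 95% limits:
- 0/30: upper limit 1 − 0.025^(1/30) = 11.6%
- 3/30: 2.1% to 26.5%
- 5/30: 5.6% to 34.7%

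Five events, an observed 17% with an upper limit near 35%, would be non-significant under two-sided Fisher.

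**Step 4: events that also occur in controls.** Vertigo, for example, can occur without an injection. The two-sided Fisher threshold then rises to 8/30 against 1/30, or 9/30 against 2/30.

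**The case against.** The strongest reply is that this attributes to the plan an analysis it does not contain. Most of that stands, and it limits the claim in four ways.

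- **Threshold.** A reader might infer that a harm must reach 6 of 30 to count. The plan names no test or sidedness, and 6 belongs to two-sided Fisher and the Yates-corrected test; 4 or 5 would do under others.
- **Unit of comparison.** Question 3 asks about adverse effects collectively. No section says that perforation, or any single harm, will be tested against Group 1. An aggregate comparison could include oral-steroid effects and background events, and the near-zero control rate is a fair assumption only for procedure-caused harm such as perforation.
- **Decision rule.** A reader might infer that real harm would be declared acceptable. The purpose sentence follows all three questions, and nothing says that non-significance on the third establishes acceptability. Could be misread is supportable; would be read is not.
- **Recording.** Nor do the documents support a reading that harms below the threshold disappear. Perforations are documented and all adverse events are reported whatever the p-value.

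It can also be said that section 11 names no analysis method for any end point, so this is one part of a wider gap. That does not remove the point. Recording and reporting do not say how question 3 is to be answered, and the criterion that is stated performs poorly under every test in the table.

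**Conclusion.** The concern holds in this limited form. Safety is framed only as a significance question in a trial sized for complete recovery, and a non-significant answer at 30 per arm would not show that the injections are acceptable. For an injection-caused harm, significance needs 4 to 6 of 30 (13% to 20%), a true 10% rate reaches it about 7% to 35% of the time, and no observed events at all would still be compatible with a rate up to 11.6%.

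This rests on 30 evaluable patients per arm, alpha 0.05 carried over from the efficacy statement, about 0/30 in Group 1, and the tests tabulated. Only the size of the shortfall depends on the choice of test.

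This is a cheap improvement. The efficacy comparison is unaffected and the harm data are already to be collected.

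**What to change.** Reword question 3 in section 5 as estimation, and add to section 11:

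- For each risk named in the Assessment of Safety section, report the rate per injected patient with an exact 95% confidence interval, for Group 2 and Group 3 separately.
- Treat any figure pooled over Groups 2 and 3 as descriptive only. Group 3 is non-randomised, takes no oral steroids and may number fewer than 30. If it did fill, 0/60 would give an upper limit of 1 − 0.025^(1/60) = 6.0%.
- For events that can occur in both randomised arms, report the Group 2 minus Group 1 difference with its 95% confidence interval.
- State that a non-significant difference will not be taken as evidence that the injections are acceptable.

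The cost is wording in two sections and a few more intervals, with no new patients, visits or data. The downside is a more modest safety conclusion than the one section 5 now aims for.
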